4.2.2 Safety Hypothesis

Primary Safety Hypothesis: VR101, when used in accordance with provided instructions for use will not result in a rate of occurrence of Serious Adverse Device Effects (SADE) greater than 1%.

P(safety) = proportion of initiated VR101 uses without a Serious Adverse Device Effect, which is equal to: Total number of initiated VR101 uses without a participant reporting a serious adverse device effect during VR101 use divided by the total number VR101 devices used.

VR101 safety will be demonstrated if the upper bound of the two-sided exact 95% confidence interval surrounding the proportion of SADE occurrence ('P(SADE)') is 0.01 or less.

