5.1.1 Study Endpoints

Used to Test Primary Efficacy Hypothesis:

1. $\Delta VHI_{VR101}(\text{day 28}) - \Delta VHI_{\text{sham}}(\text{day 28})$, the paired difference in vaginal dryness relief between VR101 and the sham control at day 28.

J3 Bioscience, Inc.	Clinical Investigation Plan and Protocol CI02	CI02-CIP Rev. 08 Page 27 of 75
	A Pivotal Clinical Investigation to Evaluate the Safety and Efficacy of J3 Bioscience Lubricating Intravaginal Ring VR101 in Relieving Symptoms of Vaginal Dryness	

Used for Validation of Claim 1:

2. The paired difference between self-reported 24-hour vaginal dryness severity reported after the first 7 days of VR101 use (see Section 5.4.5, collected at Visit 2 or 5 depending on study group) and weekly-averaged vaginal dryness severity prior to ring use (also see Section 5.4.5, collected at Visit 1 or Visit 4 depending on study group).

Used for Validation of Claim 2:

3. Participant reported ease of use of VR101 (measured on a scale of -4 to 4, see Section 5.4.6).

Used for Validation of Claim 3:

4. Self-reported perception that VR101 was comfortable during use, measured on a scale of -4 to 4 (see Section 5.4.6).

Used to Test Primary Safety Hypothesis:

5. The proportion of Serious Adverse Device Effects (SADE) in relation to the total number of VR101 devices use in the study.

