5.2 Investigational and Predicate Devices

5.2.1 Exposure to VR101 and the sham control

Participants will use VR101 for up to 17 weeks total and the sham control for 4 weeks as described above. Participants will use VR101 for approximately 13 total weeks, consecutively, to evaluate device safety.

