8 STATISTICAL CONSIDERATIONS

8.1 Summary of Statistical Methods

The hypotheses of the clinical investigation are detailed in Section 4.2. For Primary Efficacy and Validation of Claim 1, the null hypothesis will be rejected based on a two-tailed Student's t-test ($\alpha = 0.05$) or an appropriate non-parametric two-tailed test if the data do not appear to be normally distributed.

The remainder of hypotheses will be tested using the 95% confidence interval associated with a proportion of events (e.g. SADE occurrence per number of devices used, proportion of favorable survey responses).

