8.3 Statistical Power of Proposed Clinical Investigation to Demonstrate Device Safety

If, during the course of CI02, 30 participants use a total of 13 each VR101 devices (390 VR101 devices, total) during the long-term safety portion of the study, and an additional 30 participants use a total of 4 VR101 devices during the 4-week crossover efficacy portion (120 VR101 devices, total), then, at the conclusion of CI02, a total of 553 VR101 devices will have been used (510 total uses of VR101 devices in CI02, plus an additional 43 total VR101 devices already used in CI01 [with no SADEs observed in CI01]). Note that this total number of devices used does not account for VR101 devices used for less than 5 days whose data will not be used in assessing efficacy, but whose data will be included in the sample of devices used to assess safety. So, it is likely that the number of VR101 device uses evaluated for safety will exceed 553.

J3 Bioscience, Inc.	Clinical Investigation Plan and Protocol CI02	CI02-CIP Rev. 08 Page 54 of 75
	A Pivotal Clinical Investigation to Evaluate the Safety and Efficacy of J3 Bioscience Lubricating Intravaginal Ring VR101 in Relieving Symptoms of Vaginal Dryness	

If 2 SADEs occur out of a total 510 VR101 devices used according to instructions in the proposed investigation, then we will be able to rule out SADE rates greater than 1 event per 100 devices with 95% confidence. The 95% confidence interval for 2 events in 510 devices is (0.00, 0.01) (exact test, Minitab 17).

However, if no SADE is observed during the entirety of CI02 (0 events/510 devices), as expected, we will be able to rule out a SADE rate greater than 0.6 events per 100 devices with 95% confidence. The 95% confidence interval for 0 events in 510 observations is (0.000, 0.006) (exact test, Minitab 17).

Further, if no SADE is observed during the entirety of CI02 and CI01 (0 events/553 devices), as expected, we will be able to rule out a SADE rate greater than 0.5 events per 100 devices. The 95% confidence interval for 0 events in 553 observations is 0.000 (0.000, 0.005) (Minitab 17).

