8.5 Pass/Fail Criteria of the Clinical Investigation

The clinical investigation will be considered a success if the null hypotheses for the primary efficacy and safety endpoints are rejected as defined in Section 4.2.1 and 4.2.2, respectively. If these two null hypotheses are rejected, reasonable safety and efficacy of VR101 following long-term sequential use will be established and substantial equivalence of VR101 with the predicate Replens devices will be demonstrated. Results of additional hypothesis testing described in Section 4.2.3 will have no effect on the success or failure of the clinical investigation.

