8.12 Definition of Study Populations for Analysis

THE FOLLOWING STUDY POPULATIONS HAVE BEEN DEFINED FOR THIS INVESTIGATION:

Intent-to-Treat (ITT) Primary Efficacy Hypothesis Population: All patients who meet inclusion/exclusion criteria and are randomized will be included. Any missing day 0 or day 28 VHI scores will be imputed as defined in section 8.8.

J3 Bioscience, Inc.	Clinical Investigation Plan and Protocol CI02	CI02-CIP Rev. 08 Page 57 of 75
	A Pivotal Clinical Investigation to Evaluate the Safety and Efficacy of J3 Bioscience Lubricating Intravaginal Ring VR101 in Relieving Symptoms of Vaginal Dryness	

Menopausal Population: All members of the ITT population who self-report to being menopausal (have not experienced a menstrual period in the 12-month period prior to the study).

Safety Population: All VR101 devices in all study arms that are successfully inserted and used in accordance with the provided instructions for use will be included as a basis for determination of SADE proportion.

Claim 1 Population: All participants who report a daily vaginal dryness severity following their first VR101 use (Visit 2/5, depending on study arm) and report a weekly average vaginal dryness severity prior to their first VR101 insertion (Visit 1/4, depending on study arm), will be included in the analysis for Claim 1. See section 5.4.5 for relevant survey questions.

Claim 2 Population: All participants in group V1S2 who respond to the appropriate survey question (see section 5.4.6) immediately following their first VR101 insertion (Visit 1) will be included in the analysis for Claim 2.

Claim 3 Population: All daily diary responses recorded regarding VR101 comfort during use (see section 5.4.6) will be included in the analysis for Claim 3.

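### The 1% safety rule counts rings and treats rings from one woman as independent, yet section 8.5 concludes safety over long-term use, where the bound per woman is far wider

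*Combined protocol and SAP*

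**What the plan says.** The ring is the unit throughout.

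- Section 4.2.2 sets a limit of 1% and declares safety if the "upper bound of the two-sided exact 95% confidence interval surrounding the proportion of SADE occurrence" is 0.01 or less.
- Section 5.1.1, Endpoint 5: "The proportion of Serious Adverse Device Effects (SADE) in relation to the total number of VR101 devices use in the study".
- Section 8.1 gives the method as a 95% interval for "SADE occurrence per number of devices used".
- Section 8.12 defines the Safety Population by device: "All VR101 devices in all study arms that are successfully inserted and used in accordance with the provided instructions for use".

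Section 8.3 builds the planned total from the case that "30 participants use a total of 13 each VR101 devices (390 VR101 devices, total"), plus 30 women with 4 rings each (120), which makes 510. Under Rev. 08 exposure per woman can be higher: "Participants will use VR101 for up to 17 weeks total" (section 5.2.1). Section 8.4 offers the long-term part to up to 61 women.

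Section 8.5 makes this rule one of the two that decide the trial. If both are met, "reasonable safety and efficacy of VR101 following long-term sequential use will be established".

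The documents give no SADE proportion per woman, no allowance for several rings from one woman, and no reason for treating those rings as independent.

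**The concern.** An exact binomial interval takes each ring use as an independent trial. Here the uses are nested in about 60 women. Several anticipated device effects in section 13.3 (infection, irritation, adherence to the vaginal wall, inability to remove the ring) may depend on the woman as well as on the ring. This raises two separate questions.

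1. **Error rate.** If some women are prone to repeated events, the count of SADEs varies more than a binomial count. The rule may then pass too often when the true rate is 1% per ring.
2. **Meaning of the bound.** Long-term sequential use is one woman using many rings. A limit of 1% per ring does not say what share of women would have a SADE over 13 weeks, and the number of women limits what can be ruled out on that scale.

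At stake is the safety half of the trial's pass criterion, and the claim that section 8.5 attaches to it.

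**Working it through.** **Inputs.** The threshold is 0.01 with a two-sided exact 95% interval, so 2.5% in the upper tail (section 4.2.2). Ring counts are 30 × 13 + 30 × 4 = 510 (section 8.3). An upper-end Rev. 08 case is assumed in which 60 women all continue and complete: 30 × 17 + 30 × 13 = 900. Drop-outs would lower this, and so would the instruction in section 5.3.5 that V1S2 women stop when the blind is broken. The within-woman correlation ρ is not in the documents; 0.05 to 0.20 is assumed. Sections 5.3.5 and 8.3 disagree on whether partial uses count; 510 is taken as section 8.3 gives it.

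**The plan's own figures.** The exact upper bound is the p at which P(X ≤ x | n, p) = 0.025. With x = 0 it is 1 − 0.025^(1/n).

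- 0/510 gives 0.0072. Section 8.3 prints 0.006, which matches the one-sided 95% bound (0.0059).
- 2/510 gives (0.0005, 0.0141). Section 8.3 prints 0.01, which is reached only by rounding; 0.0141 fails the rule.
- 1/510 gives 0.0109, which also fails. So 510 rings pass only with no SADE.
- 3/900 gives 0.0097 and 4/900 gives 0.0113. So 900 rings pass with up to 3 SADEs.

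**Chance of passing at a true 1% per ring.** Under recurrence, each woman's own rate follows a Beta(0.01s, 0.99s) distribution with s = 1/ρ − 1, her SADE count is beta-binomial, and the counts are summed over women exactly.

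| Assumption | 510 rings (0 pass) | 900 rings (≤ 3 pass) |
|---|---|---|
| Independent rings | 0.6% | 2.1% |
| ρ = 0.05 | 1.6% | 5.7% |
| ρ = 0.10 | 2.8% | 9.7% |
| ρ = 0.20 | 6.2% | 17.2% |
| At most one SADE per woman | 0.45% | 1.5% |

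In the last row a woman with m rings has one SADE with probability 0.01m, so the expected count is still 1% of rings. At 510 rings this gives 0.87^30 × 0.96^30 = 0.0153 × 0.294 = 0.0045. At 510 rings the recurrence model crosses 2.5% between ρ = 0.085 and 0.09. At 900 rings it is already 2.7% at ρ = 0.01.

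**Bound per woman with no SADE.** This needs only independence between women.

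- 60 women: 1 − 0.025^(1/60) = 6.0% (61 women: 5.9%).
- 30 completers of 13 weeks: 1 − 0.025^(1/30) = 11.6%.
- For comparison, 510 rings: 0.72%.

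**What 1% per ring means per woman.** If rings are independent, 1 − 0.99^13 = 12.2% over 13 rings and 1 − 0.99^17 = 15.7% over 17. Under the recurrence model at ρ = 0.20 these shares fall to 6.0% and 6.8%.

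**A per-woman scenario.** Suppose 5% of 60 women truly have one SADE each. With 900 rings the rule passes with probability P(Bin(60, 0.05) ≤ 3) = 0.647, about 65%. Three such women would be 5% of 60, with an exact upper bound of 13.9%. The expected rate per ring is 3/900 = 0.33%, so passing is correct by the rule as written; it just says little about women. With 510 rings only a zero count passes, and the chance is 0.95^60 = 4.6%.

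**The case against.** The ring is a declared and consistent unit for a single-use, 7-day device, and section 8.5 mentions no proportion of women. Reading its long-term conclusion as a statement about women is interpretation. Adverse events and rings are recorded by participant, so a table by woman could be made without changing any hypothesis.

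A reader might infer three stronger things, and the documents support none of them.

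- **That the safety test has an inflated error rate.** This holds only if SADEs recur within women. A SADE under section 13.1 means death, life-threatening illness, permanent impairment, hospitalization or an intervention to prevent such outcomes, and the label in section 5.6 tells users to discontinue even for irritation. No explicit rule stops ring use after a SADE, but repeats in one woman are the less plausible case. With at most one per woman, the error is lower than under independence. At the plan's own 510 rings, even the recurrence model stays within 2.5% up to a correlation of about 0.085.
- **That clustering and the 12.2% or 15.7% of women add up to one larger harm.** Those percentages require independence. More clustering means fewer women affected.
- **That no SADE would bound the risk at 5.0% of women (0/72).** The 72 are those enrolled, and 11 withdrew during the crossover (section 8.4). An S1V2 woman who left before period 2 never used VR101.

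These points stand and limit the concern. They do not remove the gap between a bound on rings and a conclusion about long-term use.

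**Conclusion.** The concern holds as a limit on what the safety result can say. It does not show that the test is invalid.

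- The per-ring interval rests on an unstated assumption of independence within a woman. The error at a true 1% rate can exceed 2.5% if SADEs recur in susceptible women, mainly at the larger Rev. 08 exposure. It does not if each woman has at most one. The correlation is assumed and could not be estimated from a trial with no events.
- Independently of that, the bound on rings does not carry over to women. A clean result would support under 1% of rings (0.72%), but only about 6% of 60 women and about 12% of 30 women completing 13 weeks. Section 8.5 words its conclusion on the long-term scale without giving either per-woman figure.

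The plan should be changed, because this rule decides the trial, but the criterion itself can stay.

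**What to change.** 1. Keep the per-ring criterion in section 4.2.2.
2. In sections 4.2.2 and 8.3, add the proportion of women with at least one SADE on VR101, with its exact 95% interval. Give it for all women exposed to VR101 (not all 72 enrolled) and for women completing 13 consecutive weeks. Read the completer figure beside the other one, since a woman who stops because of a SADE is not a completer.
3. State in section 8.3 that the per-ring interval assumes independence between rings used by the same woman.
4. In section 8.5, word the long-term safety conclusion by the per-woman bound.

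The cost is one more exact interval in two groups and a few sentences. No new data are needed: section 12.5 logs rings by participant, and section 13 requires a form for every adverse event. The pass rule and its error rate do not change. The downside for the sponsor is a stated bound that looks less favourable: about 6% of women and 12% of completers, instead of under 1% of rings.

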4.2.3 Hypotheses for Claims and Usability Testing

If both the primary efficacy and safety hypotheses are met, then hypotheses for Claims 1, 2, and 3 will be tested using a hierarchical testing approach in order to control for multiplicity. Claim 1 will be tested first and if the null hypothesis is rejected, then Claim 2 will be tested. If the null hypothesis for Claim 2 is rejected, then Claim 3 will be tested. Refer to Appendix B for survey questions used to assess the validity of the following claims.

Claim 1: VR101 relieves vaginal dryness symptoms for up to 7 days in a majority of participants, as assessed by users.

Vaginal dryness severity will be assessed throughout the study using participant's ranked responses to questions in a questionnaire (see Section 5.4.5 below). Severity will be scored on a 0 to 3 scale (3 being the worst possible rating). At each visit, participants will be asked to rate their vaginal dryness over the last 24 hours and the last 7 days. **Claim 1 will be validated if the**

J3 Bioscience, Inc.	Clinical Investigation Plan and Protocol CI02	CI02-CIP Rev. 08 Page 25 of 75
	A Pivotal Clinical Investigation to Evaluate the Safety and Efficacy of J3 Bioscience Lubricating Intravaginal Ring VR101 in Relieving Symptoms of Vaginal Dryness	

p-value associated with a two-tailed Student's t-test of the mean of the paired values between the *daily* vaginal dryness severity score reported on day 7 (survey question, Visit 2) and average *weekly* vaginal dryness severity score reported over the week prior to VR101 use (survey question, Visit 1 for study group V1S2, Visit 4 for study group S1V2) is less than 0.05. If the paired differences are observed not to be normally distributed, an appropriate non-parametric test will be substituted for the two-tailed Student's t-test. Additionally, a two-tailed 95% confidence interval of the paired dryness values will be reported.

Claim 2: VR101 is easy to use by following the provided instructions for use.

Null and Alternative Hypotheses for Claim 2:

When the first ring is removed (Day 7, Visit 2/5 depending on study group), the participant will be asked to rate her level of agreement with the statement "the ring was easy to use by following the provided instructions" on a scale of -4 to 4 (see section 5.4.6). Claim 2 will be validated if the lower bound of the two-sided 95% confidence interval of the proportion of the study population that recorded favorable responses (participants recording a Score of 1, 2, 3 or 4) is greater than or equal to 0.80. The 95% confidence interval will be calculated using the exact test.

Claim 3: VR101 is comfortable during use.

In each daily diary, the participant will be asked to rate her level of agreement with the statement "the ring was comfortable to me today" on a scale of -4 to 4 (see section 5.4.6). Claim 3 will be validated if the lower bound of the 95% confidence interval of the proportion of the study population that recorded favorable responses (participants recording a Score of 1, 2, 3 or 4) is greater than or equal to 0.80. The 95% confidence interval will be calculated using the exact test.

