4.1.2 Validate Claims

- Claim 1: VR101 relieves the symptoms of vaginal dryness for up to 7 days.
- Claim 2: VR101 is easy to use by following the provided instructions.
- Claim 3: VR101 is comfortable during use.

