5.3.6 Number of Participants

72 participants (36 at each study site) were enrolled in CI02 with a goal of at least 60 completing the efficacy evaluation (first 11 weeks and 6 study visits) and at least 30 completing the long-term safety evaluation. Based on our drop-out rate analysis (see Section 8.4), we calculate that continuation of at least 42 participants to the long-term safety evaluation will ensure that 30 will complete the entire study. All participants will be automatically selected to participate in the long-term safety portion of the investigation.

To ensure that 60 participants successfully complete the study (and that 30 participants successfully complete the long-term safety study), it will still be possible to enroll participants to replace drop-outs at any point during the study until 60/30 participants have successfully completed the study, provided that the crossover study blind has not yet been broken (although active recruitment may discontinue when the estimated enrollment is met as described above). Note that if additional sites are used, the requirement for the minimum number of patients at each site will be modified accordingly.

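### Claim 1 asserts relief in most women but is validated by a non-directional test of the mean change, which a minority of improvers can pass

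*Combined protocol and SAP*

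**What the plan says.** Section 4.2.3 states Claim 1 as "VR101 relieves vaginal dryness symptoms for up to 7 days in a majority of participants, as assessed by users", and Appendix B (21.2) repeats that wording. The objectives in 4.1.2 state it without any reference to a majority: "Claim 1: VR101 relieves the symptoms of vaginal dryness for up to 7 days". The list of labeling claims in 1.3.2 also omits it.

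The measure is ordinal: "Severity will be scored on a 0 to 3 scale (3 being the worst possible rating"). The validation rule in 4.2.3 rests on the "p-value associated with a two-tailed Student's t-test of the mean of the paired values between the" 24-hour score at day 7 and the weekly average score before VR101 use. Claim 1 is validated if that p-value "is less than 0.05. If the paired differences are observed not to be normally distributed, an appropriate non-parametric test will be substituted". A 95% confidence interval is also reported, but validation does not depend on it. Section 8.1 repeats the same test.

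The analysis set in 8.12 is "All participants who report a daily vaginal dryness severity following their first VR101 use" and who also gave a pre-use weekly score, in either sequence. Section 5.3.6 gives the enrollment: "72 participants (36 at each study site) were enrolled in CI02 with a goal of at least 60 completing the efficacy evaluation". Section 8.4 reports 11 withdrawals during the crossover.

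Claims 2 and 3, in the same section, each define a favorable response and require an exact 95% lower bound of at least 0.80 for a proportion.

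**The concern.** A majority is a statement about how many women improve. The test asks whether the average change differs from zero. The two can disagree: a few improvers among many unchanged women can move the mean significantly while most women gain nothing. Sections 5.1.1, 5.4.5, 8.1, 8.12 and Appendix B supply no responder definition, estimated proportion or 50% threshold that would close the gap. Claim 1 is the only claim worded as a majority and the only one not tested as a proportion.

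The rule also has no direction. For the primary endpoint, the note at the end of 4.2.1 requires the mean VHI change on VR101 to be positive as well as statistically superior. Claim 1 has no matching condition.

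At stake is whether a user-reported claim can be declared validated when the trial's own data contradict its wording, and whether that declaration then opens testing of Claims 2 and 3.

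**Working it through.** **Plan's own figure.** The plan gives no sample size, power or threshold for Claim 1. Its nearest paired-t figure is the primary-endpoint power in 8.2: n = 60, difference 0.89, SD 2.14, two-sided 0.05, stated as 88%. The noncentrality is (0.89 / 2.14) × √60 = 3.22 on 59 df, which gives 88.7%. The method reproduces the plan.

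**Inputs for Claim 1.** Scores are integers from 0 to 3 (4.2.3), alpha is 0.05 two-tailed (4.2.3), and n = 72 − 11 = 61 (8.4). Because 8.12 needs only a pre-use score and one score after the first VR101, the set could be about 60 to 72. The splits into improved, unchanged and worse are illustrative assumptions, with changes of one category.

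**Mixed case: 15 improve, 3 worsen, 43 unchanged, n = 61.**
- Mean change (day 7 minus baseline) = −12/61 = −0.197.
- Variance = (18 − 12²/61)/60 = 0.2607, so SD = 0.511.
- t = −0.197 / (0.511/√61) = −3.01 on 60 df; p = 0.0038. The 95% CI is −0.33 to −0.07.
- Exact sign test on the 18 non-zero changes: p = 2 × (1 + 18 + 153 + 816)/2¹⁸ = 0.0075.
- Share improved = 15/61 = 24.6%, exact 95% CI 14.5% to 37.3%. This lies wholly below 50%, yet Claim 1 is validated under either test.

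**Boundary case: k improve, nobody worsens.** Here |t| = √[k(n − 1)/(n − k)].
- k = 3, n = 61: t = 1.76, p = 0.083, fails.
- k = 4, n = 61: t = √(4 × 60/57) = 2.05, p = 0.0445, passes with 6.6% improved.
- Exact sign test: p = 2 × 0.5^k. k = 4 gives 0.125, k = 5 gives 0.0625, and k = 6 gives 0.031. Six improvers are needed: 9.8% of 61, 10.0% of 60, 8.3% of 72.

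**Smallest number of improvers that passes when w women worsen, n = 61.**

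| w | t-test | exact sign test |
|---|---|---|
| 0 | 4 (6.6%) | 6 (9.8%) |
| 1 | 7 (11.5%) | 8 (13.1%) |
| 5 | 14 (23.0%) | 15 (24.6%) |
| 10 | 21 (34.4%) | 23 (37.7%) |

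The share needed rises as more women worsen, but stays below half throughout.

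**Direction.** Reversing the signs leaves every two-tailed p-value unchanged. Four of 61 women worsening by one category, with the rest unchanged, also gives p = 0.0445.

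**What a majority would require.** With an exact two-sided 95% lower bound above 0.50:
- n = 60: 39 improvers (65.0%, bound 0.516).
- n = 61: 39 (63.9%, bound 0.506); 38 gives 0.490.
- n = 72: 45 (62.5%, bound 0.503); 44 gives 0.489.

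**The case against.** The strongest reply is that the majority phrase is stray wording. The labeling claims in 1.3.2 and the objective in 4.1.2 omit it, and a mean test is conventional support for the claim as they state it. That stands. It is why deletion is the simplest remedy, and why a reader should not infer that the listed labeling statement itself would be contradicted by the data.

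A reader might also infer that the plan's rule simply passes when fewer than 10% of women improve. The documents do not support that as a general statement. Four changes of one category among 61 women are far from normal, so the non-parametric substitute would probably apply. Under an exact sign test four improvers fail (p = 0.125) and six are needed, which at n = 60 is exactly 10.0%. One woman worsening lifts the t-test minimum at n = 61 to 11.5%. The mismatch does not rest on that extreme, because 15 improving with 3 worsening passes both tests at 25%.

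The pilot also makes very low response look unlikely: 20 of 21 women reported dryness in the week before entry and 7 of 21 in the first week of use (2.4). This bears on how likely the problem is to arise, not on whether the rule tests the claim.

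Finally, the consequence is limited. Section 8.5 keeps claim results out of the trial's success or failure. Claim 1 is reached only after both primary hypotheses are met, and Claims 2 and 3 keep their own 0.80 bounds. The reported confidence interval would show the sign of the change. All of this stands, and it makes validation by a significant worsening a drafting gap rather than a likely result.

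**Conclusion.** The point holds. As worded in 4.2.3 and Appendix B, Claim 1 is not tested by its own rule, and the rule lacks a direction. In the illustrative case with 61 women, 25% improved is enough to validate a statement about a majority under either the t-test or the exact sign test; demonstrating a majority would take about 64% (39 of 61).

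The figures assume one-category changes, chosen splits and n = 61; the actual Claim 1 set may be anywhere from about 60 to 72. The substitute test is unnamed, so the exact sign test is an assumed stand-in. The effect stops at Claim 1 and its gate to Claims 2 and 3. It should be corrected, but it does not threaten the primary conclusions.

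**What to change.** Delete the majority phrase from Claim 1 in 4.2.3 and Appendix B, so that both agree with 1.3.2 and 4.1.2. In 4.2.3, require the significant change to be towards lower severity: the 95% CI for the mean change, day 7 minus baseline, must lie wholly below 0, or the non-parametric test must be significant in the same direction. This costs a wording amendment and a narrower claim. It needs no new data.

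If the sponsor wants to keep the majority statement, it must define a responder before the crossover blind is broken, including how women scoring 0 at baseline are counted, since they cannot improve. The definition must also take account of the two scores coming from different questions (a 7-day average before use, a 24-hour rating at day 7). Validation would then require the exact two-sided 95% lower bound of the proportion improved to exceed 0.50, for example 39/61 or 45/72. This is a harder bar. At n = 60, where 39 are needed, power is 56% if the true share is 65% and 84% if it is 70% (both shares are assumptions). It would also be a new success threshold set after much of the crossover had been run, since 8.4 already reports its withdrawals.
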